16. SAFETY OUTCOMES

All outputs for safety outcomes will be based on the Safety Analysis Set.

There will be no statistical comparisons between the treatment groups for safety data, unless otherwise specified with the relevant section.

Safety analyses will be presented separately for the different study phases (i.e., DB, Withdrawal, and OL Phases). Summaries for the DB and Withdrawal Phases will be by Overall (i.e., all subjects), AZM treated subjects (pooled), and by the individual treatments; summaries for the OL Phase will by Overall and by status of additional antihypertensive use (i.e., AZM alone and AZM plus additional antihypertensive).

For safety analysis, baseline value for the DB Phase analyses will be the last available value prior to the first dose of DB Phase study drug. Baseline value for the Withdrawal Phase will be the last available value from the DB Phase. Baseline value for the OL Phase will be the last available value prior to the first dose of DB Phase study drug.

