4.1.5 Safety

In phase 3 studies, 4814 unique adult subjects aged 18 or older with essential hypertension received AZM 20, 40, or 80 mg administered once daily. The most frequently occurring treatment-emergent adverse events (TEAEs) observed with AZM were headache, dizziness, nasopharyngitis, urinary tract infection, dyslipidemia, fatigue, blood creatine kinase increased, edema peripheral, back pain, and diarrhea. The overall rates of permanent discontinuation were generally low and similar between AZM total and placebo (9.4% and 9.0%, respectively) in the

CONFIDENTIAL

placebo-controlled monotherapy studies and between AZM total and active comparator (17.4% and 19.4%, respectively) in the long-term, active-controlled studies. No imbalances were observed between AZM and placebo or active comparator groups with respect to serious adverse events (SAEs).

With regard to clinical laboratory evaluations, increases in serum creatinine were observed with AZM treatment; the profile was consistent with the pharmacodynamic effect of AII blockade. These creatinine increases were observed in subjects with greater reductions in BP, and were generally transient or nonprogressive during treatment and reversed following study drug discontinuation. Most subjects with serum creatinine elevations were receiving coadministration with diuretics (chlorthalidone and to a lesser extent HCTZ).

AZM had no clinically meaningful effects on hematology, urinalysis, or chemistry parameters. A single dose of AZM 320 mg did not prolong QTc intervals and was well tolerated in healthy subjects.

Additional summaries of the efficacy and safety profile of AZM are provided in Sections 5.2 and 5.3 of the IB [\[18\]](#).

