9.1.8.1 Withdrawal and Follow-up of Subjects with Acute Decreases in Renal Function

Acute increases of creatinine have been described in some patients receiving agents that block the RAAS, including ACE inhibitors and ARBs. This effect is caused by inhibition of AII-mediated vasoconstriction of efferent glomerular arterioles, resulting in decreased intraglomerular pressure, and thus an acute decrease of GFR. The acute creatinine increases observed with RAAS blockade may be exacerbated under certain conditions, such as hypovolemia. Subjects who experience acute decreases in renal function (creatinine elevation of 0.5 mg/dL/44.2 umol/L from Baseline) should be evaluated by repeat testing(s) within approximately one week until resolution or stabilization. Subjects whose eGFR decreases by more than 50% or to below 20 mL/min/1.73m² (as confirmed by repeat measurement) should be withdrawn. All discontinued subjects should be followed to resolution or stabilization.

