13.1.5 Safety Analysis

Safety analyses will be presented separately for the different study phases (ie, DB, Withdrawal, and OL Phases) and where applicable, phases may be pooled together. Summaries for the DB and Withdrawal Phases will be by Overall (ie, all subjects), AZM treated subjects (pooled), and by the individual treatments; summaries for the OL Phase will be Overall and by status of additional antihypertensive use (ie, AZM alone and AZM plus additional antihypertensive). Baseline value for the DB Phase analyses will be the last available value prior to the first dose of DB Phase study drug. Baseline value for the Withdrawal Phase will be the last available value from the DB Phase. Baseline value for the OL Phase will be the last available value prior to the first dose of DB Phase study drug.

AEs will be summarized using the safety analysis set. Coding of all AEs will be performed using MedDRA. Data will be summarized using preferred term and primary system organ class. TEAEs will be defined as any AEs, regardless of relationship to study drug, that occur after the first dose of study drug and no more than 14 days (30 days for SAEs) after the last dose of study drug. TEAEs will be displayed in summary tables. Drug-related AEs will be defined as any AEs that are considered by the investigator to be related to study drug. TEAEs will also be presented by

causality (relationship to study drug) and intensity (mild, moderate, and severe). Serious TEAEs, TEAEs leading to study drug discontinuation; and all AEs leading to death will also be summarized using preferred term and system organ class.

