All the data collected for procedures (Con Meds, Vital Signs, AE assessments, Laboratory tests, Pregnancy tests) at Visit 8/ W6 will be used as visit 8/W6/last visit of DB phase in DB analysis and as WD phase baseline in WD phase analysis because all the measurements are taken before WD phase drug is given to the subjects at Visit 8/W6.

All the data collected for procedure (Con Meds, Vital Signs, Physical Examination, AE assessments, Laboratory tests, Pregnancy tests, ECG) at Visit9/ W8 will be used as visit 9/W8/last visit of WD Phase in WD phase analysis and OL baseline in OL analysis because all the measurements are taken before OL drug is given to the subjects at Visit 9/ W8.

Visit 4/Day 1 - First day of Double-Blind Dose Visit 8/Week 6 - First day of Withdrawal Phase Dose Visit 9/Week 8 – First day of Open Label Dose

LISTINGS

All listings will be ordered by the following (unless otherwise indicated in the template):

- Site-subject ID,
- Randomized treatment group (or treatment received if it's a safety output), first by active dose [by ascending dose group] and then control/placebo
- Phase
- Visit
- Date (where applicable),
- For listings where non-randomized subjects are included, these will appear in a category after the randomized treatment groups labelled 'Not Randomized'.

GENERAL DISPLAY

When a table/listing is split in multiple pages, the footnotes added to explain the table/listing should be displayed on each page of the table/listing and not only on the last one.

Document: 2014-000674-18 Statistical Analysis Plan Version 7.0

Version Number:

Version Date: 13JAN2020

7.0

Template No.: CS_TP_BS016 Revision 5 Reference: CS_WI_BS005

Effective Date: 01Apr2018

Author:

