APPENDIX 3. MARKEDLY ABNORMAL CRITERIA

LAB CATEGORY	LAB NAME	SEX	LOW CRITERIA	HIGH CRITERIA	DERIVED CRITERIA LOW (USE FOR OUTPUTS)	DERIVED CRITERIA HIGH (USE FOR OUTPUTS)
Hematology	Hemoglobin	M/F	< Baseline – 3 g/dL		<baseline -="" 30="" g="" l<="" td="">	</baseline>	
Hematology	Hematocrit	M/F	< 0.8 x Baseline		<0.8 x Baseline	
Hematology	RBC count	M/F	< 0.8 x Baseline		<0.8 x Baseline	

2014-000674-18 Statistical Analysis Plan Version 7.0 Document: Version Number: Author: Version Date: 13JAN2020

Template No.: CS_TP_BS016 Revision 5 Reference: CS_WI_BS005

Effective Date: 01Apr2018

		l .		> 20 x		I .
Hematology	WBC count	M/F	< 2 x 103/mm3	103/mm3	<2 x 10^9/L	>20 x 10^9/L
Hematology	Platelet count	M/F	< 50 x 103/mm3	> 700 x 103/mm3	<50 x 10^9/L	>700 x 10^9/L
Chemistry	ALT	M/F		>3x ULN		>3 x ULN
Chemistry	AST	M/F		>3x ULN		>3 x ULN
Chemistry	GGT	M/F		>3x ULN		>3 x ULN
Chemistry	Alkaline phosphatase	M/F		>3x ULN		>3 x ULN
Chemistry	Total bilirubin	M/F		>2.0x ULN		>2.0 x ULN
Chemistry	Albumin	M/F	<2.5 g/dL		<25 g/L	
Chemistry	Total protein	M/F	<0.8x LLN	>1.2x ULN	<0.8 x LLN	>1.2 x ULN
Chemistry	Creatinine	M/F		>1.5 x Baseline		>1.5 x Baseline
Chemistry	Sodium	M/F	<130 mEq/L	>150 mEq/L	<130 mmol/L	>150 mmol/L
Chemistry	Potassium	M/F	<3.0 mEq/L	>6.0 mEq/L	<3.0 mmol/L	>6.0 mmol/L
Chemistry	Blood Urea Nitrogen	M/F		>3x ULN		>3 x ULN
Chemistry	Calcium	M/F	<0.8x LLN	>1.2x ULN	<0.8 x LLN	>1.2 x ULN
Chemistry	Creatine kinase	M/F		>10x ULN		>10 x ULN
Chemistry	Uric Acid	М		>10.5 mg/dL		>625 umol/L
Chemistry	Uric Acid	F		>8.5 mg/dL		>506 umol/L
Urinalysis	Blood	M/F		≥1+		>=1+
Urinalysis	Glucose	M/F		≥1+		>=1+
Urinalysis	Ketones	M/F		≥2+		>=2+
Urinalysis	Casts	M/F		Any		Any
Urinalysis	Casts	M/F		Any		Any
Urinalysis	Microscopic RBCs*	M/F		≥5/hpf		>=5/hpf
Urinalysis	Microscopic RBCs*	M/F		≥5/hpf		>=5/hpf
Urinalysis	Microscopic WBC	M/F		≥20/hpf		>=20/hpf
Urinalysis	рН	M/F	<=4	>=8	<=4	>=8

Document: 2014-000674-18 Statistical Analysis Plan Version 7.0 Version Number: 7.0

Author: Version Date: 13JAN2020

Template No.: CS_TP_BS016 Revision 5 Reference: CS_WI_BS005

Effective Date: 01Apr2018

7.0

Statistical Analysis Plan

Urinalysis	Protein	M/F		>=1+		>=1+
	Specific					
Urinalysis	Gravity	M/F	<1.005		<1.005	

Document: 2014-000674-18 Statistical Analysis Plan Version 7.0 Version Number: Author: Version Date: 13JAN2020

Template No.: CS_TP_BS016 Revision 5 Reference: CS_WI_BS005

Effective Date: 01Apr2018

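### In the Withdrawal Phase, the laboratory flags defined relative to baseline use the on-drug Week 6 value, so they cannot show an abnormality that persists on AZM and reverses on placebo

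*SAP*

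**What the plan says.** SAP section 16 sets the rule for safety data: "Baseline value for the Withdrawal Phase will be the last available value from the" DB Phase. Protocol section 13.1.5 gives the same rule: "Baseline value for the Withdrawal Phase will be the last available value from the DB Phase". SAP Appendix 1 confirms that the Visit 8 data "will be used as visit 8/W6/last visit of DB phase in DB analysis and as WD phase baseline in WD phase analysis". For the DB Phase the "baseline value for the DB Phase analyses will be the last available value prior to the first dose of DB Phase study drug", and SAP section 16 gives the OL Phase that same pre-treatment reference.

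SAP Appendix 3 defines marked abnormality. The creatinine criterion is ">1.5 x Baseline", with no absolute limit and no multiple of the upper limit of normal. Three haematology criteria are also relative to baseline: a haemoglobin fall of more than 30 g/L, haematocrit below 0.8 times baseline, and red cell count below 0.8 times baseline.

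Other planned outputs bear on the point. Protocol section 13.1.5 and SAP section 16.2 provide absolute values and changes by visit and shift tables against the reference range. SAP section 16.2 adds a by-visit count of children with elevated creatinine, but does not define elevated. SAP section 16 plans no between-group tests on safety data unless otherwise specified.

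**The concern.** Safety and tolerability relative to placebo is a secondary objective (Protocol section 5.1.2), and the Withdrawal Phase is the only phase that randomises AZM against placebo. Protocol section 4.1.5 describes the creatinine rises seen in adults as "generally transient or nonprogressive during treatment and reversed following study drug discontinuation". A rise of that kind gives a Week 8 to Week 6 ratio near 1 in children who stay on AZM, and below 1 in those switched to placebo. Neither ratio exceeds 1.5, so the Withdrawal flag table is blind to the pattern that the protocol leads one to expect. A stable 1.6-fold rise would be flagged in the DB Phase, vanish from the Withdrawal table and, under SAP section 16, be flagged again in the OL Phase if it persisted. A reader who sees almost no flags in either Withdrawal arm could take that as evidence of no difference.

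**Working it through.** The documents give no expected creatinine flag rate, so there is no plan figure to reproduce. The check has two parts: arithmetic on the plan's own limits, and a simulation with assumed inputs.

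**1. A persistent rise (illustrative values, mg/dL).** Day 1 0.60, Week 6 1.00, Week 8 1.00.
- DB flag: 1.00 / 0.60 = 1.67, flagged.
- Withdrawal flag: 1.00 / 1.00 = 1.00, not flagged.
- Week 8 against Day 1: 1.00 / 0.60 = 1.67, would be flagged.

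**2. A first crossing at Week 8.** Day 1 0.60, Week 6 0.84, Week 8 0.96, with Week 4 also below the limit.
- DB flag: 0.84 / 0.60 = 1.40, not flagged.
- Withdrawal flag: 0.96 / 0.84 = 1.14, not flagged.
- Week 8 against Day 1: 0.96 / 0.60 = 1.60, would be flagged.

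**3. The bound, with no assumed rates.** A value can sit at the limit in each phase without exceeding it.
- Creatinine: 1.5 × 1.5 = 2.25 times Day 1. If eGFR is inversely proportional to creatinine, the fall is 1 − 1/2.25 = 56%.
- Haematocrit and red cell count: 0.8 × 0.8 = 0.64 times Day 1.
- Haemoglobin: 30 + 30 = 60 g/L below Day 1.

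**4. Simulation.** 1,000,000 children were re-randomised 1:1 at Week 6. The assumptions, none from the documents, were: within-child CV 5, 10 or 15%; 2, 5 or 10% of children with an AZM-induced rise of about 1.7-fold; 50% or 100% reversal on placebo by Week 8.

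| Creatinine flag at Week 8 | AZM | Placebo | Difference (points) |
|---|---|---|---|
| Week 6 baseline, central case (CV 10%, 5% affected, full reversal) | 0.20% | 0.19% | 0.0 |
| Day 1 baseline, central case | 4.0% | 0.2% | 3.8 |
| Week 6 baseline, whole range | | | 0.0 to 0.3 |
| Day 1 baseline, whole range | | | 0.9 to 8.5 |

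Of AZM children above 1.5 times Day 1 at both Week 6 and Week 8, only 0 to 1.3% are flagged on the Week 6 baseline. First crossings at Week 8 occur in 0.04 to 2.2% of AZM children, and 75 to 100% of these go unflagged. The upper end comes from CV 15%, where much of it is measurement noise: the placebo arm itself then shows about 2.7% against Day 1 with full reversal.

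**5. Mean change.** In the central case, AZM minus placebo is 0.000 − (−0.022) = 0.022 mg/dL from Week 6, and 0.022 − 0.000 = 0.022 mg/dL from Day 1. The contrast is the same, and the SD of change is smaller from Week 6 (0.095 against 0.138).

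**6. Scale.** Protocol section 13.3 gives 52 per arm, so 3 × 52 = 156 on AZM. After 10% dropout and 1:1 re-randomisation, 156 × 0.9 / 2 ≈ 70 continue AZM and about 70 take placebo after AZM. In the central case the Day 1 flag would show 70 × 4.0% = 2.8 children against 70 × 0.2% = 0.14. An affected rate of 2 to 10% corresponds to about 1 to 7 children.

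**The case against.** The strongest reply is that the Week 6 baseline is deliberate and sound. Protocol and SAP agree on it, it matches the reference point of the primary endpoint, and re-randomisation at Week 6 balances that value in expectation. Mean change from Week 6 is therefore an unbiased contrast in which reversal on placebo appears as a fall. Shift tables can show high-to-normal on placebo against high-to-high on AZM wherever values leave the reference range. All of this stands.

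A reader might go further than the point made here and infer that the whole renal comparison with placebo is pushed to the null, or that affected children are lost from the report. The documents do not support either. The DB table flags any creatinine above 1.5 times the pre-treatment value at Week 4 or Week 6. Section 9.1.8.1 of the protocol runs independently of the reporting baseline: it requires repeat testing after a creatinine rise of 0.5 mg/dL, which a 2.25-fold value reaches from any starting level of 0.4 mg/dL or more (1.25 × 0.4 = 0.5). It also has a withdrawal rule, beginning "Subjects whose eGFR decreases by more than 50" per cent. No safety test is planned, so no inference is biased.

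Three things remain. The DB table has no placebo arm. A mean dilutes a rise confined to a few children: 0.022 mg/dL with SD 0.095 and 70 per arm has a standard error of 0.095 × √(2/70) ≈ 0.016, so the signal is about 1.4 standard errors. And the elevated-creatinine count, which might have filled the gap, has no definition.

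**Conclusion.** The point holds for the categorical flags. In the Withdrawal Phase the four baseline-relative criteria cannot show an abnormality that arose on AZM, persists on AZM and reverses on placebo. One that first crosses the Day 1 limit at Week 8 can go unflagged in both blinded phases, up to 2.25 times Day 1 for creatinine. That bound follows from the plan's limits alone and is a corner case. The flag differences of 0.0 to 0.3 against 0.9 to 8.5 percentage points rest wholly on assumed rates, variability and reversal.

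It does not hold for the renal comparison as a whole, because means, absolute values and shift tables remain informative. This is a gap in reporting, not in clinical monitoring. It is a cheap improvement rather than a flaw that threatens the trial.

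**What to change.** In SAP section 16.2 and Appendix 3, keep the Week 6 baseline and every existing summary. Add a Week 8 count of the four baseline-relative flags against the last value before the first DB dose, by Withdrawal arm.

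- Split the placebo group by prior DB treatment (AZM or losartan). The SAP lists a single Withdrawal placebo group, and the exclusion of losartan-treated children is stated only for efficacy, so unreversed rises from losartan could otherwise be counted there.
- Add a footnote that abnormalities continuing from the DB Phase are included.
- In section 16.2, define elevated creatinine and state which baseline, if any, it uses.
- Reconcile the OL baseline. SAP section 16 says: "Baseline value for the OL Phase will be the last available value prior to the first dose of DB Phase study drug". Appendix 1 instead labels the Week 8 data as the OL baseline.

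The cost is one derivation and one more table, in which abnormalities with onset in the DB Phase appear a second time. No new data are needed and no clinical rule changes.

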16.1. ADVERSE EVENTS

Adverse Events (AEs) will be coded using Medical Dictionary for Regulatory Activities (MedDRA) central coding dictionary, Version 20.0 or higher.

Treatment emergent adverse events (TEAEs) are defined as AEs that started or worsened in severity on or after the first dose of study medication and no more than 14 days (30 days for SAEs) after the last dose of study drug. TEAEs will be defined within each study phase.

Document: 2014-000674-18 Statistical Analysis Plan Version 7.0

Version Number:

7.0

Template No.: CS_TP_BS016 Revision 5

Version Date:

13JAN2020

Author:

Reference: CS_WI_BS005

Effective Date: 01Apr2018

For the DB Phase, TEAEs will include events whose date of onset occurred after the first dose of double-blind study drug and before the first dose of withdrawal study drug, or within 14 days (30 days for serious AEs) after the last dose of the double-blind study drug for subjects who did not enter the withdrawal study phase.

For the Withdrawal Phase, TEAEs will include events whose date of onset occurred after the first dose of withdrawal study drug and before the first dose of open-label study drug, or within 14 days (30 days for serious AEs) after the last dose of the withdrawal study drug for subjects who did not enter the open-label study phase. For those subjects who switched from AZM to Placebo in WD phase, all AEs occurred on the first 3 days of WD period will be attributed to AZM.

For the OL Phase, TEAEs, will include events whose date of onset occurred after the first dose of open-label study drug and within 14 days (30 days for serious AEs) after the last dose of the open-label study drug. See Appendix 2 for handling of partial dates for AEs. In the case where it is not possible to define an AE as treatment emergent or not, the AE will be classified by the worst case; i.e. treatment emergent.

An overall summary of number of subjects within each of the categories described in the sub-section below, will be provided as specified in the templates.

Listings will include all AEs (TEAEs and Non-TEAEs).

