10.1.7 Relationship to Study Procedures

Relationship (causality) to study procedures should be determined for all PTEs and AEs.

10.1.8 The relationship should be assessed according to causality scale in Section 10.1.6. Start Date

The start date of the AE/PTE is the date that the first signs/symptoms were noted by the subject and/or physician.

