APPENDIX 2. Partial Date Conventions

Imputed dates will NOT be presented in the listings.

ALGORITHM FOR TREATMENT EMERGENCE OF ADVERSE EVENTS:

START DATE	STOP DATE	ACTION
Known	Known	If start date < study med start date, then not TEAE If start date >= study med start date, then TEAE
	Partial	If start date < study med start date, then not TEAE If start date >= study med start date, then TEAE
	Missing	If start date < study med start date, then not TEAE If start date >= study med start date, then TEAE
Partial, but known components show that it cannot be on or after study med start date	Known	Not TEAE
	Partial	Not TEAE
	Missing	Not TEAE
	J	
Partial, could be on or after study med start date	Known	If stop date < study med start date, then not TEAE If stop date >= study med start date, then TEAE
	Partial	If Informed consent year and AE start year is same and study med start year is later, impute start date to informed consent date. If study med start year and AE start year is same, impute start date to study med start date If study med start year is earlier then 2016, impute the start date to first day of the year Impute stop date as latest possible date (i.e. last day of month if day unknown or 31st December if day and month are unknown), then: If stop date < study med start date, then not TEAE If stop date >= study med start date, then TEAE
	Missing	Assumed TEAE
Missing	Known	If stop date < study med start date, then not TEAE If stop date >= study med start date, then TEAE

Document: 2014-000674-18 Statistical Analysis Plan Version 7.0

Version Number:

Version Date:

7.0 13JAN2020

Template No.: CS_TP_BS016 Revision 5

Reference: CS_WI_BS005

Effective Date: 01Apr2018

Author:

START DATE	STOP	ACTION
	DATE	
	Partial	Impute stop date as latest possible date (i.e. last day of
		month if day unknown or 31st December if day and
		month are unknown), then:
		If stop date < study med start date, then not TEAE
		If stop date >= study med start date, then TEAE
	Missing	Assumed TEAE

ALGORITHM FOR MEDICATION HISTORY / CONCOMITANT MEDICATIONS:

START DATE	STOP DATE	ACTION
Known	Known	If Informed consent date > medication end date ≥ Informed consent date -30, assign as Medication History
		If start date >= study med start date, assign as concomitant
	Partial	Impute stop date as latest possible date (i.e. last day of month if day unknown or 31st December if day and month are unknown), then:

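### SAP 16.1 gives conflicting boundary rules for adverse events dated on the first-dose day of a phase (Day 1, Week 6, Week 8)

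*SAP*

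**What the plan says.** SAP 16.1 first defines TEAEs as events that "started or worsened in severity on or after the first dose of study medication", with an upper limit of 14 days after last dose (30 for serious events). It then adds that "TEAEs will be defined within each study phase". SAP Appendix 2 uses the same inclusive bound for known start dates: "If start date >= study med start date, then TEAE".

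The three phase sentences in SAP 16.1 are worded differently:

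- DB Phase: "events whose date of onset occurred after the first dose of double-blind study drug and before the first dose of withdrawal study drug".
- Withdrawal Phase: "events whose date of onset occurred after the first dose of withdrawal study drug and before the first dose of open-label study drug".
- OL Phase: "events whose date of onset occurred after the first dose of open-label study drug", up to the 14- or 30-day limit.

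On how onset is recorded, Protocol 10.1.8 says: "The start date of the AE/PTE is the date that the first signs/symptoms were noted". Protocol 10.2.1.2 lists start and stop dates among the items documented for each event and mentions no clock time. SAP 16 presents safety separately for each phase. SAP 16.1 sends all AEs, treatment-emergent or not, to the listings.

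**The concern.** The phase sentences are strict at the lower end and, for DB and Withdrawal, strict at the upper end too. Compared as dates, an event on the first-dose day is neither after that dose nor before it. The same section and its appendix call that event treatment-emergent, so two programmers following different sentences would produce different by-phase tables.

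The days concerned are the ones on which treatment changes. Day 1 brings the first active dose. At Week 6 subjects are re-randomized to continue or to switch to placebo. At Week 8 everyone starts open-label AZM, so former losartan subjects receive AZM for the first time. These first doses are given in clinic (Protocol 9.3.4.1, 9.3.4.5 and 9.3.5), so part of the calendar day follows dosing. A reaction soon after a first dose would carry exactly the date on which the rules disagree.

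**Working it through.** The plan states no figure on this point, so the check assigns each calendar day to a phase under each set of rules.

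**Inputs**

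- First DB dose: Day 1 (SAP 6.1 and Appendix 1).
- Week 6: the example in SAP 14.1 puts the day before Week 6 at Day 42, so Week 6 = 42 + 1 = Day 43.
- Week 8: the Withdrawal Phase lasts 2 weeks, so Week 8 = 43 + 14 = Day 57.
- Onset known by date only (assumption, from Protocol 10.1.8 and 10.2.1.2).
- The subject enters all three phases. The last OL dose date does not affect the result.

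**Assignment of onset day d**

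| Phase | Strict phase sentences | Days covered | On or after own first dose, before next | Days covered |
|---|---|---|---|---|
| DB | 1 < d < 43 | 2 to 42: 41 of 42 | 1 ≤ d < 43 | 1 to 42: 42 of 42 |
| Withdrawal | 43 < d < 57 | 44 to 56: 13 of 14 | 43 ≤ d < 57 | 43 to 56: 14 of 14 |
| OL | d > 57 | from 58 | d ≥ 57 | from 57 |

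Under the strict sentences, Days 1, 43 and 57 fall in no phase. All three satisfy d ≥ 1, so all three are TEAE days under the general definition and Appendix 2. With the inclusive lower bound, no day is unassigned and none is counted twice.

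**Does any other text settle the phase?**

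- *Appendix 2* compares onset with the study medication start date and does not say whether that is the overall or the phase-specific date. SAP 6.1 ties the reference start date to Day 1. On that reading, Week 6 and Week 8 events are TEAEs but still have no stated phase.
- *The worst-case default* in SAP 16.1 decides whether an unclear event is treatment-emergent. It does not choose the phase or treatment column.
- *The three-day rule* in SAP 16.1 attributes AEs in the first 3 days of the withdrawal period to AZM for subjects switched from AZM to placebo. Appendix 1 names Week 6 as the first withdrawal dosing day, so this rule appears to treat Week 6 as inside the phase, contrary to the strict sentence. It is silent on losartan-to-placebo subjects, on those who continue active drug, and on Day 1 and Week 8.
- *Appendix 1* gives adjoining phases the same boundary visit. It uses the Visit 8 and Visit 9 AE assessments, made before the new drug is given, as the last visit of the earlier phase.
- *Protocol 13.1.5* also places TEAEs after the first dose, so it does not supply the inclusive bound.

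**Illustration under the strict reading only.** One day is 1/42 = 2.4% of the nominal DB Phase and 1/14 = 7.1% of the Withdrawal Phase. These are shares of days. They would be shares of events only if onset were uniform over the phase, which nothing in the documents supports.

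**The case against.** The strongest reply is that the SAP, read as a whole, already includes these events. The inclusive definition is followed directly by the statement that TEAEs are defined within each phase, which invites applying the inclusive bound phase by phase. Appendix 2 is the working algorithm, and it is inclusive. The phase sentences say what is counted; they do not say that nothing else is. In ordinary language, dizziness two hours after a clinic dose does come after that dose. The gap appears only if the rule is coded as onset date later than dose date, which the SAP does not prescribe. If the eCRF captures onset time, the rule can be applied by time and the gap closes.

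Most of this stands. A reader might infer that first-dose-day events will be removed from the safety tables and survive only in listings. The documents do not support that. The inclusive texts point towards keeping them, the three-day rule read with Appendix 1 treats Week 6 as part of the withdrawal period, and SAP 16.1.4 separately summarizes all AEs leading to death and discontinuation, whether or not treatment-emergent.

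The reply does not remove the contradiction, and none of these texts states which phase receives a Week 6 or Week 8 event. A written phase rule that conflicts with the general definition is more than a missing detail.

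**Conclusion.** The point holds as an internal inconsistency in SAP 16.1 that leaves the handling of events on three first-dose days to the programmer. Strictly applied to dates, the phase sentences place Days 1, 43 and 57 in no phase and could omit those events from the by-phase TEAE tables. The inclusive rules keep the events but leave their phase, and therefore their treatment column, unclear at Weeks 6 and 8. It matters most at Week 6, where the column may be active drug or placebo.

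No number of lost events can be stated. The 2.4% and 7.1% day shares are illustrative and apply only to the strict reading. It would also be wrong to say that every event occurring within hours of a first dose is lost, because that presupposes the strict coding. The conclusion rests on onset being held by date only, which the protocol indicates but which could not be checked against the eCRF. The correction is worth making before the tables are programmed.

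**What to change.** In SAP 16.1, write each phase sentence as: onset date on or after the date of the phase's first dose, and before the date of the next phase's first dose. Where there is no next phase, the upper limit is 14 days after last dose (30 for serious events), as now. Then:

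- State in Appendix 2 that the comparison date for phase assignment is the first-dose date of the phase.
- State how the three-day AZM rule fits: whether the Week 6 dosing day is the first of the three days, and in which phase and treatment column such events are tabulated.
- Reconcile the date rule with Appendix 1, which treats the pre-dose AE assessments at Visits 8 and 9 as belonging to the earlier phase. An exception for events already present before dosing is workable only if the eCRF records that; otherwise the plain date rule should apply.

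The cost is about one sentence per phase plus these clarifications, with no new data. The downside is that a few events beginning before the dose on a dosing day, including Day 1, will be counted in the newly started phase.
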